10.3 Schedule of assessments for each visit

Patients will undergo assessments as per normal standard of care and the schedule will not be changed due to this study.

10.4 Follow up Procedures

The follow-up procedures will be as per normal standard of care for 5 years and the schedule will not be changed due to this study. We will obtain relevant clinical information from the medical records.

10.5 End of Study Definition

The patient recruitment for the initial pilot study will be one year from the commencement of the study at Guy's Hospital. We will assess whether the endpoints and outcomes are met at the end of the pilot study but the patients will be followed up for their long-term treatment outcome and survival as per normal standard of care. We will continue to obtain relevant information on patients' treatment and survival outcome from patients' medical records. The end of the study definition for the pilot study (year 1) is the end of 12 months' period after the commencement of the study regardless of the number of patients recruited. We will submit the protocol for a major amendment towards the end of year 1 so that SOTO study will continue as a prospective observation study for up to additional 4 years of recruitment if further funding is obtained. If no further funding is obtained

by the end of year 1, we will end the patient recruitment and the study. We will analyse all data and produce the final study report at the end of second year.

The criteria for progression beyond year 1 pilot study are set as below:

- 1) More than 50% of the approached participants will consent to taking part in SOTO study
- 2) At least 30% of the tissue samples will be successfully used to generate organoids
- 3) Further funding is obtained to continue beyond year 1

11 Laboratories

The fresh tissue samples will be provided by the head and neck biobank at Guy's Hospital to be processed for organoids within 72 hours at [name] laboratory at Kings College London and the blood samples will be processed according to standard laboratory SOP at [name] laboratory at Kings College London. Plasma and saliva samples will also be processed to assess ctDNA in the future. The additional biological samples including oral swab, urine or stool samples if obtained will be stored at Guy's Hospital head and neck biobank under the custodial of [name], biobank manager (HTA licence is 12121; the Licence Holder is [name]). Further details on the sample collection, processing, storage and analysis will be provided in the laboratory manual.

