4 List of Abbreviations and Definitions

(Delete as appropriate)

| AE | Adverse Event |
|-------------|--|
| AR | Adverse Reaction |
| ASR | Annual Safety Report |
| СА | Competent Authority |
| CI | Chief Investigator |
| CRF | Case Report Form |
| CRO | Contract Research Organisation |
| DMC | Data Monitoring Committee |
| EC | European Commission |
| GAfREC | Governance Arrangements for NHS Research Ethics Committees |
| ICF | Informed Consent Form |
| MA | Marketing Authorisation |
| MS | Member State |
| Main REC | Main Research Ethics Committee |
| NHS R&D | National Health Service Research & Development |
| PI | Principal Investigator |
| QA | Quality Assurance |
| QC | Quality Control |
| Participant | An individual who takes part in a clinical trial |
| REC | Research Ethics Committee |
| SAE | Serious Adverse Event |
| SDV | Source Document Verification |
| SOP | Standard Operating Procedure |
| SSA | Site Specific Assessment |
| TMG | Trial Management Group |
| TSC | Trial Steering Committee |

5 Summary/Synopsis

| Trial Title | Prospective study to correlate the treatment sensitivity of patient-derived organoids with clinical outcomes in head and neck squamous cell carcinoma (HNSCC) patients | |
|--|--|--|
| Internal ref. no. (or short title) | SOTO: treatment Sensitivity of Organoids to predict Treatment Outcome in head and neck cancer patients | |
| Protocol Version number and Date | Version 1.1 14 th March 2022 | |
| Study Phase if not mentioned in title | NA. It is an observation study | |
| IRAS Number | 305689 | |
| REC Reference | 22/NW/0023 | |
| Study Duration | 1 year of recruitment followed by standard of care follow-up for 5 years | |
| Sponsor name | King's College London | |
| | Guy's and St. Thomas Foundation | NHS trust (co-sponsor) |
| Chief Investigator | [name] | |
| Funder | Guy's and St Thomas' (GSTT) charity via a generous philanthropic donation from [name] and [name] | |
| Medical condition or disease under investigation | Head and neck squamous cell carcinoma (HNSCC) | |
| | Objectives | Endpoints |
| Primary | To assess the success rate of generating organoids from tissues in patients with HNSCC | Rates of successful organoid cultures |

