8.1 Study Design

This is a prospective observation study to generate patient-derived organoids from patients' samples to assess treatment response and to correlate with patients' treatment outcomes. We would first do a pilot study during year 1 to establish the pathways required and to assess the success rate in generating patient-derived organoids. During this time, we will also assess the willingness of patients to participate in the study, as well as that of clinicians to help recruitment. In addition, the time required to generate HNSCC organoids and to assess treatment response in order to correlate with patients' outcome will be evaluated during year 1.

Primary endpoint and outcome

Primary endpoint

The percentage of successful organoid samples generated from the tumour samples obtained

Primary outcome

The ability to generate organoid cultures successfully from tumour samples

Secondary endpoint and outcomes

Secondary endpoints

1) To determine the IC50 doses and dose response curves of radiotherapy, cisplatin or carboplatin chemotherapy and their combination of PDOs

2) To correlate the IC50 doses and dose response curves above with the recurrence rates and disease-free survival of patients

3) To correlate IC50 doses and dose response curves above with the complete metabolic response (PET-CT) and residual disease or salvage neck dissection

4) To correlate IC50 doses/dose response curves above with the objective response rates of patients undergoing same systemic treatment

Secondary outcomes

1) The ability of these treatment(s) to decrease tumour growth and kill the organoids ex-vivo (number and size of alive organoids after treatments)

2) The ability of the PDOs to predict recurrences and survival outcome of these patients based on the radiosensitivity and chemosensitivity of the PDOs

3) The ability of the organoids to predict complete metabolic response and treatment outcome of patients

4) The ability of the organoids to predict response to the same systemic treatments that the patients are receiving systemic treatments

Exploratory endpoints and outcomes

Exploratory endpoints

1) To correlate the IC50 doses/dose response curves with plasma ctDNA before and after treatment

2) Immunohistochemistry (IHC) staining, exome sequencing and RNA sequencing of PDOs and patients' samples

3) The IC50 doses of various targeted therapies based on actionable genetic mutations

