8.2 Treatment visits

This is an observation study and the patients will continue their clinical visits and follow-up for 5 years as per normal standard of care. We will obtain the treatment outcome from medical records of patients.

9 Subject selection

This will be a single centre study performed at King's College London and Guy's and St Thomas' NHS foundation trust.

We will have several cohorts of HNSCC patients undergoing standard of care treatments, which we plan to include:

- 1) 10 patients with surgically resectable locally advanced disease, followed by adjuvant radiotherapy +/- chemotherapy
- 2) 5 primary radiotherapy +/- concurrent chemotherapy
- 3) 5 recurrent or metastatic HNSCC undergoing platinum based chemotherapy +/- cetuximab or immunotherapy.

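### The final report is due at the end of year 2 but outcomes are collected for 5 years, so disease-free survival would be finally reported on immature data and no later analysis is named

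*Protocol*

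**What the plan says.** Section 10.5 fixes several times. The end of the pilot "is the end of 12 months' period after the commencement of the study regardless of the number of patients recruited", and endpoints are to be assessed at that point. If no further funding has been obtained "by the end of year 1, we will end the patient recruitment and the study". The next sentence is "We will analyse all data and produce the final study report at the end of second year". With funding, recruitment may go on for up to 4 more years, but only after a major amendment.

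Follow-up is much longer. The synopsis gives the study duration as "1 year of recruitment followed by standard of care follow-up for 5 years". Section 8.2 says "the patients will continue their clinical visits and follow-up for 5 years as per normal standard of care", and section 10.4 says "The follow-up procedures will be as per normal standard of care for 5 years". Section 10.5 itself adds: "We will continue to obtain relevant information on patients' treatment and survival outcome from patients' medical records".

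The endpoint that needs this follow-up is secondary endpoint 2 in section 8.1: "To correlate the IC50 doses and dose response curves above with the recurrence rates and disease-free survival of patients". It belongs to cohort 1, which section 9 sets at 10 of the 20 patients. Section 10.1 explains that tumour response cannot be observed directly after resection, and asks whether a lower organoid IC50 goes with longer DFS. Recurrence and DFS are therefore the only clinical outcomes named for this cohort. The protocol gives no landmark time or minimum follow-up for them.

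**The concern.** A report that is called final and covers all data is normally the one that answers the study's questions. Here it falls well before the follow-up that the protocol plans to collect. For the largest cohort, the link between organoid sensitivity and outcome would be settled on a minority of the intended observation time. The remaining years of recurrence and survival data would be abstracted from records with no stated analysis to receive them. A reader of the year-2 report could take an absence of correlation as evidence about the organoids when it may only reflect how few events had occurred.

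**Working it through.** The protocol has no event or power calculation to reproduce. Section 15 says that none was done for year 1.

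**Follow-up at the cut (no hazard assumption)**
- Inputs: recruitment over months 0 to 12 and final report at month 24 (section 10.5); follow-up of 60 months (synopsis, sections 8.2 and 10.4).
- First patient: 24 − 0 = 24 months from entry. Last patient: 24 − 12 = 12 months. Under uniform entry the mean is 18 months.
- Share of planned follow-up: 12/60 = 20% to 24/60 = 40%.
- Planned follow-up after the report: 60 − 24 = 36 months at least, and 60 − 12 = 48 months for the last patient.
- The last patient would complete 5 years at about month 12 + 60 = 72.

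These spans run from enrolment. A DFS clock that starts later, for example at surgery, makes them shorter.

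**Expected recurrences in cohort 1 (illustration)**
- Inputs: 10 patients (section 9). Section 6 says up to 50% may recur and gives no time horizon. The 5-year horizon, uniform entry and the shape of the hazard are assumptions.
- Model: P(recurrence by month t) = 1 − exp(−ln 2 × (t/60)^k), which gives 50% at 60 months, averaged over t = 12 to 24.
- Constant hazard (k = 1): 1 − [60/(12 × ln 2)] × (0.5^0.2 − 0.5^0.4) = 1 − 7.21 × (0.8706 − 0.7579) = 0.187.

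| Hazard shape | Mean P by the cut | Events in 10 | Events in 10 at 5 years |
|---|---|---|---|
| k = 1 (constant) | 0.187 | 1.9 | 5 |
| k = 0.7 | 0.257 | 2.6 | 5 |
| k = 0.5 (strongly front-loaded) | 0.314 | 3.1 | 5 |

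Starting the DFS clock 3 months after enrolment lowers these to 1.6, 2.3 and 2.9. With 30% rather than 50% recurring by 5 years and no lag, the range is 1.0 to 1.8, against 3. Only recurrences are counted. Deaths without recurrence, if they count as DFS events, would add to both columns.

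**What a later cut would buy**
- Illustrative Schoenfeld power for a median split on IC50, hazard ratio 3 (assumed), two-sided 0.05: Φ(½ × √d × ln 3 − 1.96).
- d = 2: Φ(0.777 − 1.96) = 12%. d = 3: Φ(0.951 − 1.96) = 16%. d = 5: Φ(1.228 − 1.96) = 23%.

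The later cut makes the data mature but does not make the cohort adequately powered.

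**The case against.** The strongest defence starts from the funding condition. The year-2 sentence follows directly on the case where funding fails, so it need not govern a funded continuation, whose analysis times an amendment can set. A reader might infer that a year-2 final report contradicts 4 more years of recruitment, but the text does not require that reading. The point that remains is narrower. The unfunded course is the one this version fully governs; in it, 5-year collection still stands and no analysis uses it. The funded course names no later DFS analysis either.

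The date also has a plausible origin. The pilot ends at month 12, and section 16.1 requires a final report to the ethics committee within a year of the end of the trial, which gives month 24. Nothing in the protocol forbids later use of the data. That explains the date, but the report is still described as final and as covering all data.

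A reader might infer that year 2 is the only analysis time. It is not: section 10.5 also sets an assessment at the end of the pilot and separates it from long-term outcome. That assessment comes earlier still, so it does not help DFS.

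A reader might also apply the 30% organoid success figure to the 10 patients and conclude that about 3 would contribute to the correlation. The documents do not support this. The figure is a minimum per tissue sample, and section 10.1 allows surgical patients both a biopsy and a resection sample. If two samples succeeded independently at 30% (an assumption), the patient-level yield would be 1 − 0.7² = 51%.

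Finally, a DFS landmark may be left to an analysis plan that is not at hand, and section 7 seeks only preliminary data. Both are fair. But the protocol itself sets the date of the final report, and that date does not fit its own follow-up period.

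**Conclusion.** The point holds as a mismatch between the report date and the follow-up period, with a limited consequence. Followed as written without further funding, the cohort 1 correlation with recurrence and DFS would be finally reported at 20% to 40% of planned follow-up, and at least 36 months per patient would enter no stated analysis. Those figures need only the protocol's own dates and recruitment spread over the 12 months. The count of about 2 to 3 recurrences against 5 is an illustration that depends on 50% recurring by 5 years and on the assumed timing.

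The primary endpoint (organoid success), the progression criteria and the cohort 2 PET-CT at 3 months after treatment are largely unaffected. A reader might infer that moving the analysis would rescue the DFS question. It would not: with 10 patients no firm DFS conclusion is possible at either date. The gain is that the final statement rests on mature data and that the data collected are used.

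**What to change.** In section 10.5, call the year-2 document the pilot (or end-of-pilot) report. State that its recurrence and DFS results are interim and descriptive, with median follow-up given. Name one later DFS analysis, done when every patient has reached a fixed follow-up (for example 5 years, at about month 72), and say that it applies with or without further funding. As the unfunded course also ends the study, the wording should make clear that outcome abstraction from records continues until that analysis.

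The cost is a few sentences of protocol text and one re-run on data already planned for collection. The small downside is that the final DFS answer comes later.

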11.1 Data Recording/Reporting

All staff that would directly deal with the human tissues or blood will undertake HTA training.

11.2 Sample Receipt/Chain of Custody/Accountability

Handling of the samples upon arrival at the laboratory needs to be documented. Upon receipt of the samples, the laboratory should ensure that the physical integrity of these samples have not been compromised in transit. If it has, it is important that the study teams, as well as the sponsor, are informed of this. Upon receipt of samples laboratory staff should ensure that all samples are accounted as per the labeling. All samples received should be logged in an accountability log.

11.3 Sample Transfer to sites outside the Organisation

Individual informed consent will be obtained from the patients to specify whether they would agree for their samples to be transferred to collaborating third parties including overseas and commercial laboratories on behalf of KCL. This may include but not be limited to validation of research results.

The patient samples and derived organoids (with linked data) may be shared with collaborating laboratories, nationally or internationally, for the purposes of facilitating the research aims. Specific agreements will be put in place as required by the Sponsor including material transfer agreements where necessary. Any commercialisation of the results of this study will be specified in contractual arrangements between parties where necessary and participants will be informed that they would not benefit financially.

12 Assessment of Safety

This is an observation study and the patients participated in this study will undergo routine treatments and the safety of the treatments will be assessed as per standard of care.

12.1 Ethics Reporting

No serious adverse events are expected to occur following the tissue sampling involved in this study, as they will be done during standard care procedures. Participants will be followed-up by their treating clinicians as per normal practice.

12.2 Ethics & Regulatory Approvals

Study protocol and other documentation will be submitted to the North West - Greater Manchester South Research Ethics Committee for ethical approval.

13 Compliance and withdrawal

13.1 Subject compliance

We will monitor the percentage of approached participants who consent to taking part in the study during the first year of recruitment.

13.2 Withdrawal / dropout of subjects

We will monitor the percentage of participants who withdraw consent from the study after taking part. Since the primary outcome is the rate of successful generated organoids and will not be affected by the dropouts of subjects, we will not need to recruit more participants to back fill those who may have withdrawn or dropped out once the fresh tissues are obtained from patients following consent.

13.3 Protocol Compliance

The patients will undergo routine treatments as per standard of care. We will monitor whether we will miss the blood samples from patients during specific time points.

14 Data

14.1 Data management

As this is an observation study, we will collect data from patients that are already available in the hospital record on patients' demographics, smoking and alcohol history, tumour characteristics including HPV status, proposed treatment plans. The patients' treatment details, treatment responses, recurrences and survivals will also be obtained from clinical record. They will be recorded on paper Case Report Forms (CRFs). Participant files and paper CRFs will be identified using a Participant Identification Number. Personal information will not be stored on CRFs. Screening and enrolment logs will be maintained by the research team. For enrolled participants, identifiable patient data will be stored in an Excel file for the purposes of gathering follow-up data. This file will password protected and stored on the KCL secured network, whereby access is only granted by the PI to named individuals. Paper CRFs, consent forms and the Trial Master File will be stored in locked filing cabinets within the Oral Clinical Research Unit (KCL, Guy's Hospital, London, UK). Data generated from laboratory processes related to the generation of PDOs and subsequent testing will

be kept in the research laboratory. These data will be identified with the PIN and no personal data will be used in the lab records.

Data linkage

If the participating patients have come from or will move to different health care providers, we will attempt to get either available archival tissues and/or data from the relevant health care providers after sending them the relevant patients' consent forms. We may also go to the central national databases with a patient's NHS number to get clinical data if necessary.

15 Statistical considerations

The first year of recruitment will serve as a pilot study for this observation study and no formal power calculation is performed for year 1. The number of patients chosen for each cohort is the expected number of patients that we anticipate to recruit within 12 months based on the number of HNSCC patients that we treat at Guy's. We expect more than 50% of the approached participants will consent to taking part in SOTO study and at least 30% of the tissue samples will be successfully used to generate organoids. A successful pilot study in year 1 will be defined as one that meets the pre-defined expectation. The data from year 1 pilot study will be used to calculate the sample size required to extend the observation study beyond year 1, which will be submitted as a major amendment.

16 Ethical considerations

16.1 Research Ethics Committee (REC) review & reports

Before the start of the trial, approval will be sought from an NHS REC for the trial protocol, informed consent forms, patient information sheet, and GP information letters.

Any amendments to the protocol or study documents will be reviewed by the Sponsor, sent to the REC for review and approvals. No changes will be implemented until approval has been received from the REC and approved by the Trust R&D department, if required.

All correspondence with the REC will be retained in the Trial Master File.

An annual progress report (APR) will be submitted to the REC within 30 days of the anniversary date on which the favourable opinion was given, and annually until the trial is declared ended. The Chief Investigator's will approve the annual report which will be submitted by the CI or delegate.

The Chief Investigator will notify the REC of the end of the trial within 90 days of the end of the study. If the trial is ended prematurely, the Chief Investigator will notify the REC, including the reasons for the premature termination.

Within one year after the end of the trial, the Chief Investigator will submit a final report with the results, including any publications/abstracts, to the REC.

16.2 Peer review

This study has been previously peer reviewed when an application for was submitted to the GSTT charity for the funding of this study.

